Presenting to a healthcare facility with symptoms of wheezing and shortness of breath can initially complicate diagnosis and treatment for asthma exacerbation or COVID-19.⁴ Currently, the available case study evidence is unclear whether those with asthma are at greater risk or overrepresented among cases with severe COVID-19 outcomes.¹⁴⁻¹⁷ Recent US data has shown higher rates of asthma in hospitalized COVID-19 patients compared to COVID-19 patients in the ambulatory setting.¹⁸ Further, in one US cohort study, asthma was the second most common co-morbidity after obesity among those 18-49 years old with COVID-19.¹⁹ It is also unclear if individuals with asthma are overrepresented among those currently seeking testing for COVID-19 across the nation. While cardiovascular disease, kidney disease, and diabetes have been associated with greater COVID-19, mortality²⁰ pulmonary conditions such as asthma, which is exacerbated by respiratory viruses, have not been well studied in COVID-19.

Residential asthma triggers. Adults ordinarily spend about 15 hours/day indoors^{11,12} and since COVID-19, those hours have largely been spent in their homes. Environmental asthma triggers in residential settings include dust mites, animal dander, mold, moisture, tobacco smoke, particulates, cockroach allergen, mouse/rat allergens, VOCs, and nitrogen dioxide.^{13,21,22} Indoor residential air quality has been associated with decreased general health, asthma symptoms, airway inflammation, asthma exacerbations and decreased lung function in adults with asthma.²³⁻²⁶ We will focus on residential VOCs, specifically disinfectants/cleaners, and particulates as potential asthma environmental triggers exposures increased during the COVID-19 pandemic.

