Disinfectants. The CDC recommends initially cleaning residential surfaces with soap and water followed by disinfecting surfaces with an EPA-registered household disinfectant.⁵ As of August, 2020 the EPA includes 482 products that meet the EPA criteria for use against SARS CoV-2 virus. Information listed by the EPA includes product name, active ingredients, contact times required, formulation types (e.g., ready-to-use, wipes, dilutable), and use sites (residential, institutional, healthcare). There are 305 products listed for use in any setting, 16 products listed only for residential use, 33 for institutional/residential use, and 4 for healthcare/residential use. Many of the products listed as appropriate for residential use have active ingredients shown to be asthmagenic such as quaternary ammonium (195 products) and sodium hypochlorite (56 products).²⁷ The EPA list provides no guidance regarding potential respiratory impacts of these products.

The effects of disinfectants on adults with asthma have been widely explored in the occupational context; research specific to residential exposures and disinfecting/cleaning products is limited. Exposure to cleaning agents, disinfectants, and hand sanitizers at worksites has been shown to increase asthma related symptoms and exacerbations.²⁸⁻³⁶ In residential settings, weekly use of spray cleaners was associated with asthma in adults^{9,37,38} and with decreased FEV₁ and FVC in European adults.³⁹ The odds of current asthma for women using bleach 4-7 times per week were 3.0 (1.5-7.1) compared to never using bleach.¹⁰ Specific chemicals in cleaning/disinfecting products shown to impact asthma include d-limonene⁴⁰ terpenes, formaldehyde,^{41,42} chloroform,⁴³ quaternary ammonium compounds,^{31,44} amine compounds, and aldehydes.⁴⁵ Other VOCs commonly found in cleaners/disinfectants include ethanol, acetone, propanol, and a-pinene.⁴⁶ Our work in asthma and older adults revealed that, compared to those with well controlled asthma, participants with very poorly controlled asthma cleaned their bathrooms more often with products determined to have respiratory impact ($p=0.02$).⁴⁷ While cleaners and disinfectants are known asthma triggers, the extent asthma is impacted when use is increased during a pandemic is unknown.

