EMA is a survey approach which uses repeated sampling of participants to capture behaviors and experiences in a real time context. This methodological approach maintains the ecological validity of reported behaviors and decreases the impact of recall bias as surveys are sent periodically to participants through electronic devices.⁶¹ EMA is particularly useful when trying to understand the context around symptoms or behaviors. Available literature that combines the EMA methodology with asthma research focuses primarily on asthma-related outcomes such as symptoms, control, quality of life, history, and medication adherence and their relationship with stress (perceived stress, mood, hassles, social support).⁶²⁻⁶⁴ None of the published literature to date pairs EMA with indoor air quality and asthma symptoms. The ability to timestamp behaviors, events, experiences, whether they present a positive or negative health impact, is valuable when seeking to understand the complexity of multiple risk factors and multiple environmental and behavioral interactions.

Exposure	Sensor	Range/ Accuracy	Optimal range
VOCs	Multi-pixel metal oxide semiconductor gas sensor	0-60,000 ppb/ $\pm 10\%$	<333ppb
PM _{2.5}	Laser-based light scattering particle sensor	0-1,000 $\mu\text{g}/\text{m}^3$ / $\pm 15\mu\text{g}/\text{m}^3$ or 15%	<15 $\mu\text{g}/\text{m}^3$

Awair Omni Indoor Air Quality Monitor® continuously monitors about 1,000 square feet of indoor air for 7 air quality factors: total VOC, PM_{2.5}, temperature, humidity, CO₂, ambient light, and ambient noise. This feasibility study will only focus on VOCs and PM_{2.5} levels (Table 1). The Awair Omni measures about 4"X4"X1.3", is wi-fi and Bluetooth enabled, plugs into a standard AC outlet, and includes an 8-hour battery back-up. An air quality reading is taken every 10 seconds and real-time data are uploaded to a dashboard accessed only by research personnel. The display on the Awair Omni will be limited to VOCs and PM_{2.5} data. Our preliminary work with Awair indoor air quality monitors indicates that increased VOC levels are detected when disinfectants are used and increased PM_{2.5} levels are detected when vacuuming without a

[figure not shown]
[figure not shown]
vacuum cleaner.

HEPA filter. The Awair proprietary dashboard provides secure communication between the Awair Omni and its dashboard. Data will be exported from the dashboard to a .CSV file.⁶⁵⁻⁷¹

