We will also assess the duration the indoor air quality monitor is used by each participant. The quantitative participant feasibility assessment of acceptability, appropriateness, and feasibility will be analyzed descriptively. In addition, we will examine differences in use/acceptance by participant characteristics (e.g., age, asthma symptoms, overall health, education, etc). Qualitative interview data will be transcribed, uploaded into Dedoose qualitative analysis software for content analysis.

Aim 2a: We will collect baseline data on the current frequency and degree of disinfectants/cleaners and exposure to environmental triggers (e.g., secondhand smoke). We will capture real-time self-reported data on disinfectant use throughout the study period. We will determine the prevalence of disinfectant/cleaner use and frequency (% EMA prompts at which disinfectant/cleaner use is reported). We will obtain data from the Awair dashboard to determine the number of times VOCs and PM_{2.5} levels exceed optimal levels, average daily levels, average levels per time period, and fluctuations in VOC and PM_{2.5}. We will identify possible environmental triggers that contribute to high levels of VOCs and PM_{2.5} leading to event-contingent prompts.

[figure not shown]
Aim 2b: We will determine baseline level of asthma control as measured by the ACT. We will use EMA to determine the level of asthma control over the study period as indicated by (a) asthma symptoms reported at each prompt and over the 14 days; (b) number of time-periods during which an EMA prompt is sent and participants report asthma symptoms; and (c) lung function as measured by FEV₁% predicted at each prompt. Asthma control will also be evaluated using EMA by exploring differences in variability in lung function.

Aim 3: Data collected using the EMA approach are multilevel with time windows (level 1) nested with individuals (level 2). The exposure variables will include: (1) Baseline self-reported use and frequency of disinfectant/cleaner use and PM_{2.5} exposures; (2) Number of times VOC and PM_{2.5} levels exceed the threshold for the optimal readings per week; and (3) Average scores of VOC and PM_{2.5} levels in the time windows considered in the analysis. The outcome variables we will consider include occurrence of any asthma symptoms, inhaler use, and FEV₁% predicted (within 30 minutes of each EMA prompt).

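### Total VOC is a non-specific proxy for disinfectant exposure with no stated detection rate by product, and Aim 3 has no other time-varying measure of disinfectant use

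*Combined protocol and SAP*

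**What the plan says.** - **Link between VOC and disinfectants.** Significance (Residential asthma triggers): "We will focus on residential VOCs, specifically disinfectants/cleaners, and particulates".
- **Sensor.** Table 1 gives the VOC channel as a "Multi-pixel metal oxide semiconductor gas sensor". It yields a total in ppb, with 333 ppb as the upper limit of the optimal range. The device description restricts the study to VOC and PM2.5. It reports preliminary work in which VOC readings rose with disinfectant use, without product class, number of tests or detection rate.
- **Chemicals of concern.** Significance (Disinfectants) gives as examples "active ingredients shown to be asthmagenic such as quaternary ammonium (195 products) and sodium hypochlorite (56 products". It continues: "Specific chemicals in cleaning/disinfecting products shown to impact asthma include d-limonene", followed by terpenes, formaldehyde, chloroform, quaternary ammonium compounds, amines and aldehydes. Then: "Other VOCs commonly found in cleaners/disinfectants include ethanol, acetone, propanol, and a-pinene".
- **Product counts.** The same section: "As of August, 2020 the EPA includes 482 products that meet the EPA criteria for use against SARS CoV-2 virus" and "There are 305 products listed for use in any setting, 16 products listed only for residential use, 33 for institutional/residential use", plus 4 for healthcare/residential use.
- **Self-report.** Under EMA survey items, the two random daily prompts ask about disinfectant or cleaner use in the past 2 hours and, if there was any, its type and brand. Under Procedures, the triggered survey is sent only when VOC or PM2.5 leaves the optimal range.
- **Analysis.** Aim 2a reports momentary use as a percentage of prompts. Aim 3 lists three exposure sets: baseline self-report; VOC and PM2.5 exceedances per week; and "Average scores of VOC and PM_{2.5} levels in the time windows considered in the analysis".

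**The concern.** The study's central question is whether heavier disinfectant use worsens asthma control. The within-person part of Aim 3 can answer it only through exposures that change over the 14 days, and all of those are sensor readings. A total-VOC reading does not identify a compound or a source, and the documents do not show how it responds to bleach or quaternary-ammonium products. If some uses leave the reading unchanged, those periods enter the model as low exposure.

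The gap also reaches data collection. The triggered survey, its spirometry request and the 30-minute follow-up all depend on an exceedance. The stated ambitions go beyond feasibility: the Significance section expects guidance on home disinfectant use, the Summary foresees an effect on recommendations, and the Specific Aims feed a powered study. A null VOC association could be taken as reassurance about products that the sensor may not have registered.

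**Working it through.** The plan states no figure for the sensor's detection of disinfectant use, so there is none to reproduce. Four checks follow.

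**1. Which Aim 3 exposures vary over time?**
- Baseline self-reported use: fixed within a participant.
- VOC and PM2.5 exceedances per week: vary by week, from the sensor.
- VOC and PM2.5 averages per time window: vary by window, from the sensor.
- Momentary reported use, type and brand: collected, but not listed. No analysis under Aims 1 to 3 names type or brand.

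**2. How prominent are the two highlighted actives among listed products?** The 195 and 56 counts follow a statement about products suitable for residential use. I therefore take the residential total as denominator, assuming that products for any setting include homes and that the four categories do not overlap.
- Residential-usable products: 305 + 16 + 33 + 4 = 358.
- Full overlap of the two actives: 195 / 358 = 54.5%.
- No overlap: (195 + 56) / 358 = 251 / 358 = 70.1%.
- If the counts referred instead to all 482 products: 195 / 482 = 40.5% to 251 / 482 = 52.1%.

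These are shares of a product list. They say nothing about how often each product is used or how much VOC it gives off.

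**3. How much use is asked about without an exceedance?** Two random prompts with a 2-hour look-back cover at most 2 × 2 = 4 of the 16 hours from 6 a.m. to 10 p.m., or 25%.

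**4. What would imperfect detection do?** This is an illustration with assumed inputs. For a binary exposure with non-differential misclassification, the share of the true risk difference that remains is PPV + NPV − 1. With prevalence p, sensitivity Se and false-positive rate F:
- PPV = p·Se / [p·Se + (1 − p)·F]
- NPV = (1 − p)(1 − F) / [(1 − p)(1 − F) + p(1 − Se)]

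With use in p = 0.20 of windows:
- Se 0.95, F 0.05: 0.826 + 0.987 − 1 = 0.81
- Se 0.80, F 0.20: 0.500 + 0.941 − 1 = 0.44
- Se 0.50, F 0.20: 0.385 + 0.865 − 1 = 0.25
- Se 0.30, F 0.20: 0.273 + 0.821 − 1 = 0.09

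For Se 0.50 and F 0.20, the share runs from 0.15 at p = 0.10 to 0.31 at p = 0.30. The planned models use continuous averages and a logit link for symptoms, so this shows the direction and possible scale of the loss. It does not predict it.

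**The case against.** The strongest case for the plan has five parts.

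- **VOCs matter in their own right.** Bleach and quaternary ammonium are given as examples only. The same section names d-limonene, terpenes, formaldehyde and chloroform as affecting asthma, and hand sanitizers among worksite exposures linked to symptoms. A VOC rise from sanitizer is therefore not simply a false alarm. This stands.
- **The sensor responds.** The preliminary work saw VOC rise with disinfectant use, and a product may register through its co-ingredients. This stands, as far as one unquantified statement can carry it.
- **Self-report runs in parallel.** Use is recorded at baseline and at random prompts, the triggered survey asks about sources, and Aim 2a looks for contributors to high readings. This stands in part. A search that starts from exceedances can show that a high reading had another source, but it cannot show a use that caused no exceedance. The momentary reports enter no association model.
- **Any check by product class will be rough.** The text does not describe recording the time of use. The monitor sits in one room at a time, and proximity to it is asked only in triggered surveys. Use elsewhere in the home would look like non-detection. This stands and limits what the check can claim.
- **This is a feasibility study and Aim 3 is exploratory.** This stands and sets the weight of the point.

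A reader might infer that the VOC channel cannot represent disinfectant exposure at all, because hypochlorite contains no carbon and quaternary ammonium is a salt. The documents do not support that. They give no sensor response for these products, and the preliminary work points the other way for disinfectants as a group. A reader might also take 54.5% to 70.1% as the share of uses missed. It is a share of listed products, and the share of uses missed could be near zero.

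**Conclusion.** The concern holds in this form: total VOC is a non-specific proxy with no stated detection rate by product class, and Aim 3 offers no other time-varying measure of disinfectant use. A null VOC association could not be read as no effect of disinfectants, and a positive one could not be credited to a particular product.

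The size of the loss cannot be derived from the documents. Under the assumed inputs above, between 9% and 81% of a true risk difference would remain. The conclusion does not need the sensor to miss bleach or quaternary ammonium; it needs only that its detection of them is unknown. The change should be made because it uses data already being collected and strengthens Aim 3. It does not threaten the feasibility objectives.

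**What to change.** 1. **Aim 3.** Add reported disinfectant or cleaner use in the last 2 hours, from the random prompts, as a level-1 exposure beside VOC. Where counts allow, add product class as an exploratory term: hypochlorite, quaternary ammonium, alcohol, other. Code class from type and brand, using the product list that the protocol already cites. Keep reports from triggered surveys separate, because they exist only after an exceedance.
2. **Aim 2a.** Tabulate, by product class, the share of reported uses with a VOC rise or exceedance in the same 2-hour look-back. Present it as a descriptive check only. State that the order of use and reading may be unknown, and that distance from the monitor cannot be separated from non-detection.
3. **Interpretation.** The Specific Aims and the device description already call the measure total VOC. Carry that term through to the Aim 3 results and conclusions, and do not describe the reading as disinfectant exposure.

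The cost is the coding of product names, one table and one or two model terms. Cells by class will be small. The reported-use term will also be missing for much of the day: two random prompts fall in at most two of the four daily periods.

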As individuals are sheltering at home for longer periods of time, those with asthma may increasingly contend with household asthma triggers and new chemical exposures as they sanitize their home environments to prevent COVID-19. Household asthma triggers may include air pollutants^{6,7} such as air particulate matter in the form of combustible pollutants such as secondhand smoke⁸ and use of different chemical cleaning/disinfecting products.^{9,10} Tight housing construction results in less well-ventilated homes and enhanced exposure to household air pollutants. Ordinarily, adults can spend as many as 15 hours per day indoors^{11,12} which further contributes to their risk for environmental exposures. The current COVID-19 crisis has altered usual cleaning practices and amount of time spent at home. It is unknown how these changes impact adults with asthma.

We will assess the feasibility and usability of ecological momentary assessment (EMA) to capture the context of real time behaviors and environmental exposures that impact indoor environments. In addition, we will assess the feasibility and usability of providing participants with a readily available indoor air quality monitor (Awair Omni®) to continuously capture total volatile organic compounds (VOCs) and particulates (PM_{2.5}). This design will allow us to alert participants of high levels and collect real time data on exposures and asthma symptoms. Daily and exposure-related lung function will be measured with a low-cost home spirometer. Finally, we will examine the effect of residential environmental exposures that may be related to increased time spent at home due to COVID-19 and the associations between these exposures and asthma control.

Our team is comprised of three nurse-scientists and a physician-scientist, each of whom have research focused on asthma experienced in a range of age groups from adolescent to older adult. Our team has established community partners (Chicago Asthma Consortium) and our research team members are situated in three different midwestern US areas. Our long-term goal is to characterize the impact of COVID-19 on existing asthma risk factors so as to develop tailored, home-based asthma interventions that takes into account COVID-19 and are responsive to the changing home environment and change in home routines resulting from this pandemic. For adults with sub-optimally controlled asthma, this study will:

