We will use multi-level binary logistic regression to examine the associations of the exposure variables with the binary outcome variables. We will use multilevel linear regression to examine the associations of the exposure variables with FEV₁% predicted. We will control for level 1 variables (time of day, day of week) and level 2 variables (baseline asthma symptoms, demographic characteristics, and psychosocial characteristics). Using available time stamps from the indoor air quality monitor, EMA, and the spirometer, we will also explore average lag time between an event-contingent prompt and self-reported asthma symptoms using multilevel survival analyses.

Summary

The proposed study has several strengths. First, our study is innovatively addressing the increased use of disinfectants during COVID-19 in adults with asthma. The study builds on an ongoing study and will be conducted with individuals who have agreed to be recruited for future studies and facilitate recruitment. Furthermore, participants will be drawn from a wide geographic area in the US which increases broad representation of participants. Moreover, we will uniquely gather real time environmental exposure data and indicators of asthma control in unregulated indoor residential space without actual in-person contact. Finally, findings from this study have the potential to impact recommendations for indoor use of disinfectants/cleaners for those with asthma and will guide further research.

References

1. Center for Disease Control and Prevention. Asthma. FastStats web site. <https://www.cdc.gov/nchs/faststats/asthma.htm>. Published 2018. Accessed Date.
2. Center for Disease Control and Prevention. AsthmaStats. https://www.cdc.gov/asthma/asthma_stats/default.htm. Published 2020. Accessed Date.
5. Center for Disease Control and Prevention. Coronavirus (COVID-19). <https://www.cdc.gov/coronavirus/2019-nCoV/index.html>. Published 2020. Accessed Date.

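### The Aim 3 models leave out indoor humidity and temperature, which the monitor already measures; a paired sensitivity analysis would be a cheap addition

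*Combined protocol and SAP*

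**What the plan says.** The Awair Omni paragraph under Data collection methods says the device covers "7 air quality factors: total VOC, PM_{2.5}, temperature, humidity", with CO2, light and noise completing the seven. On recording it says "An air quality reading is taken every 10 seconds and real-time data are uploaded to a dashboard accessed only by research personnel", with later export to a CSV file. It does not say which channels that file contains. The scope is then narrowed: "This feasibility study will only focus on VOCs and PM_{2.5} levels (Table 1").

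In Data Analysis, Aim 3, the sensor-based exposures are the weekly count of VOC and PM2.5 exceedances and "Average scores of VOC and PM_{2.5} levels in the time windows considered in the analysis". For adjustment the plan states "We will control for level 1 variables (time of day, day of week"), plus person-level terms for symptoms at baseline, demographics and psychosocial measures. Humidity, temperature and CO2 appear nowhere in the analysis plan, as exposures or as covariates.

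Two background statements bear on this. Under Residential asthma triggers in Significance: "Environmental asthma triggers in residential settings include dust mites, animal dander, mold, moisture". In Specific Aims: "Tight housing construction results in less well-ventilated homes and enhanced exposure to household air pollutants".

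**The concern.** The protocol treats moisture as something that can provoke asthma, and the monitor measures humidity alongside VOC and PM2.5. If humidity or temperature also moves with VOC or PM2.5 inside a home, the Aim 3 coefficients for the two pollutants would carry some of that effect.

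The two window-level covariates would not remove it fully. Time of day can absorb a daily cycle that participants share. Day of week can absorb a weekly pattern. With 14 days of collection each weekday occurs twice (14/7 = 2), so a damp or hot spell of a few days in one home is not a weekday effect.

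Aim 3 is exploratory, but the protocol means to use it: as preliminary data for a powered study of interventions (Specific Aims) and, in the Summary, as possible input to advice on disinfectant use indoors. A reader of those results would want to know whether a pollutant coefficient survives adjustment for conditions recorded by the same device.

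**Working it through.** The plan states no power, effect size or correlation for Aim 3, so there is no figure to reproduce. The check has two parts.

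**1. Text against text**
- Measured by the monitor: VOC, PM2.5, temperature, humidity, CO2, light, noise.
- Used in Aim 3: VOC and PM2.5 only.
- Window-level adjustment: time of day and day of week.
- Humidity: tied to asthma through moisture in the trigger list. No link to VOC or PM2.5 is stated.
- Temperature: tied to neither asthma nor pollutant levels in the text.
- Ventilation: described as affecting pollutant exposure. No separate route to symptoms is stated, and no passage says CO2 marks ventilation.

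**2. Illustration of size (assumed values)**

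Inputs from the documents: 50 participants, 14 days, four periods a day, so at most 50 × 14 × 4 = 2,800 windows. Only three prompts a day are scheduled (one morning, two random), which gives 50 × 14 × 3 = 2,100 before event prompts and non-response. Half of 2,800, or 1,400, serves as a lower case.

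Assumed: ρ, the correlation of the omitted factor with the pollutant given the other covariates; γ, its standardised effect on FEV1% predicted; no true pollutant effect; independent windows; two-sided 5% test.

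- Bias = ρ × γ, in SD of outcome per SD of pollutant.
- SE ≈ 1/√n: 0.0189 for n = 2,800.
- False-positive rate = Φ(bias/SE − 1.96) + Φ(−bias/SE − 1.96).
- Variance inflation from adding the covariate = 1/(1 − ρ²).

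Worked case, ρ = 0.3 and γ = 0.1: bias = 0.03; 0.03/0.0189 = 1.587; Φ(−0.373) + Φ(−3.547) = 0.355; inflation = 1/(1 − 0.09) = 1.10.

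| ρ | γ | Bias (SD) | False positives, n = 2,800 | False positives, n = 1,400 | Variance inflation |
|---|---|---|---|---|---|
| 0 | any | 0 | 5.0% | 5.0% | 1.00 |
| 0.1 | 0.05 | 0.005 | 5.8% | 5.4% | 1.01 |
| 0.3 | 0.10 | 0.03 | 35.5% | 20.2% | 1.10 |
| 0.5 | 0.20 | 0.10 | about 100% | 96.3% | 1.33 |

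For the binary symptom outcome the same product is only approximate on the log-odds scale. With an assumed effect of 0.3 log-odds per SD, ρ = 0.3 gives 0.09 (odds ratio 1.09), ρ = 0.5 gives 0.15 (1.16), and ρ = 0 gives no bias.

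**The case against.** The strongest reply is that this is a declared choice. Significance explains the focus on VOCs and particulates as exposures raised by the pandemic, Aim 3 only explores associations, and nothing confirmatory rests on it. That stands, and it keeps the point minor. It does not settle the point, because the scope statements define which exposures are of interest and give no reason to leave the other readings out as covariates.

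A reader might infer something stronger: that the protocol itself identifies humidity, temperature and ventilation as time-varying common causes of exposure and symptoms, and then contradicts itself by ignoring them. The documents do not support that. As set out above, moisture is given only as a trigger and ventilation only as a cause of exposure; the ventilation remark also concerns how homes are built, which is largely fixed over 14 days.

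A reader might also infer that adding these variables to the main models is free. It is not. Under Procedures, an alert triggers a survey, and mitigation is asked about 30 minutes later; Aim 1 counts how often the environment was modified. If mitigation includes airing the room, a 4-hour mean of humidity or temperature may partly be a consequence of the alert or of symptoms, and adjusting for it could add bias. This objection stands and shapes the fix.

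Finally, attribution to disinfectants does not rest on sensor coefficients alone: random surveys record recent product use, and event surveys ask about likely sources. That softens the concern without removing it for the VOC and PM2.5 coefficients themselves.

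**Conclusion.** The point holds as a cheap improvement of minor severity. Humidity and temperature are measured, moisture is a named trigger, and the Aim 3 window-level adjustment contains neither variable, so part of a VOC or PM2.5 association could reflect them. Humidity has the better support in the text; temperature is included because it comes from the same device at little extra cost, not because the protocol links it to asthma.

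The size is unknown. It runs from nothing, if the omitted factor is uncorrelated with the pollutant, to large under the strongest assumed values, and the documents give nothing that places the study in that range. The false-positive rates also rest on independent windows and on window counts that may not be reached. They show why a check is worthwhile; they do not estimate the bias in this study. No inconsistency in the plan is claimed.

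**What to change.** - Confirm that humidity and temperature can be exported from the dashboard, and keep both channels. If they cannot be, state the lack of adjustment as a limitation.
- Leave the planned Aim 3 models as they are. Beside each, pre-specify a sensitivity version with relative humidity and temperature as level 1 covariates.
- Average both over a stated interval of readings ending before the alert or prompt; where a window contains an alert, end it before the first one. At one reading every 10 seconds an hour holds 360 readings, so a short interval is enough. This keeps out mitigation prompted by that alert, though not carry-over from an earlier window.
- Fit both versions to the same windows and report the VOC and PM2.5 coefficients with and without the two covariates.
- Treat CO2 as optional, with its rationale written down, since its use as a ventilation marker is not stated in the documents.

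Cost: a few more export columns and some time alignment. The loss of precision is slight at modest correlation (inflation 1.10, so a standard error about √1.10 = 1.05 times as large at ρ = 0.3) and greater at ρ = 0.5 (1.33, about 1.15 times). Participant procedures and the device display do not change.
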